3b	Descriptive: focus groups	Focus groups: Participants in the control arm of the RCT (N~60)	Descriptive, thematic analysis to examine post-intervention perceptions related to the Fitness Tracker use, usefulness and impact on overall health
3c	Descriptive: in-depth interview	In-depth interview: Participants in the intervention and control arms of the RCT (N~20)	Descriptive, thematic analysis to examine perceptions related to the recruitment process and research participation to the RCT

C. Aim 1: Build a functional app for HIV self-management linked to a smart pill (Wise App) for PLWH and assess its usability

C.1. Intervention Components.

Medication adherence can be monitored using the CleverCap™ Lite bottle, which emits a cellular signal when it is opened, allowing for near real-time acquisition of data regarding patient pill taking activity. The CleverCap™ Lite adherence monitor (see Compliance Meds Technologies, North Miami Beach, Florida) communicates dosing behavior in real-time by transmission of a patient identifier and date-time stamp over existing cellular networks when the container is opened to take medications.

The primary intervention component will include:

- Medication Reminders – Reminders will be tailored to participants' medication schedule (*Figure 1*). To avoid notification fatigue, a cellular signal is sent to the phone when the servers detect a pill bottle opening, which prevents the launching of the reminder notifications on the phone. The app will launch an in-phone pop-up alert before a scheduled dose time is missed. If the Wise App does not receive notification that the pill bottle has been opened, additional reminders will be launched on the phone after the scheduled dose, asking the patient to taken their medication.

Additional app components are listed below and organized according to Fogg's Functional Triad:

Figure 1. Medication Schedule

[figure not shown]

Figure 2. Mobile App Screen of User History

- **Missions (Tool)** – Missions are intended to help users keep track of activities they enjoy. This feature will display a checklist of tasks participants aim to complete (e.g. go to the gym, text/email a friend, etc.)

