Participants must be at least 18 years old, have a diagnosis of HIV, speak and understand English or Spanish, and live in the US. Participants must have a smartphone and be on ART medications. Our participants will all be Medicaid eligible and most of our participants, as can be seen from our preliminary work, are from racial and ethnic minority groups.

To comply with the AHRQ Policy on the Inclusion of Priority Populations (NOT-HS-03-010), our study participants are chronically ill, inner-city, low-income and minority. We anticipate that about 40% of our study participants will include women.

In addition, participants must report past 30 days adherence of 80% or less as measured using the Visual Analogue Scale (VAS)⁶⁷ (Appendix) or have a viral load of over 400 copies/mL. Exclusion criteria are: participation in any other mobile app study for PLWH, not including text messaging studies, and any clinical problems that would not allow someone to use a cell phone. Prior to participating in any study procedure, participants must voluntarily provide informed consent.

D.3. Recruitment Plan.

We will post flyers at each of the recruitment sites listed below and will provide compensation for time that it takes to complete the study questionnaires. The flyer will have the name, contact number, and e-mail for the study coordinator. PLWH from these sites are almost exclusively from low socioeconomic backgrounds. If we are unable to recruit participants after posting flyers, we will then hand distribute flyers to potential participants in the waiting rooms of our sites. We will also be using advertisements through social media that will lead users to a short Qualtrics survey, The Wellness Study Interest Survey, asking for contact information and some eligibility criteria. The purpose of this short survey is to attract more individuals towards our study, provide them with necessary study-related information, and to determine initial eligibility before a staff member reaches back out to screen for enrollment eligibility. Our main sites for recruitment are those where we have previously conducted our studies (HRSA H97HA08483, NINR P30NR010677-03S1 and CDC U01PS003715-01).

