Following the completion of the baseline study instruments, study participants in both arms will be given a CleverCap™ Lite dispenser and trained on how to use it, as well as a fitness tracker that will be synced to Wise App. Study participants in both arms will be trained by study team members on how to use the different features of the Wise App. Those in the intervention group will receive medication reminders while those in the control group will receive reminders about completing their step goal. Participants in both arms will be given a document that includes contact information for the project team, information about compensation, study reminders, and will also receive a telephone call from a research assistant 1 week after enrollment to assist with any technical problems with the app or the CleverCap™ Lite dispenser and biweekly thereafter.

Participants will be texted appointment reminders for study visits via Qualtrics. Hard to reach participants will also be sent scheduling reminders through the Qualtrics system and encrypted e-mails from the study's secure CUMC e-mail address.

Token of appreciation: Participants will be given \$40 at the baseline visit, \$50 + up to an extra \$25 for app challenges completed at the 3 month visit, and \$60 + up to an extra \$25 for app challenges completed at the 6 month visit (up to a total of \$200 for participation) and for providing a blood sample (or recent lab results) for viral load/ CD4 testing and completion of study questionnaires. Participants will also have the option to have the cost of their transportation to and from the study site paid for, through a ridesharing service.

D.8. Operationalization of Outcome Measures.

The primary outcome will be ART adherence, measured by the CleverCap™ dispenser. The CleverCap™ dispenser will automatically record each time a participant opens the dispenser. We will collect adherence data each day from the start to the end of trial (day 1 to 6 months), and it is a count response (number of times taking medication each day). Frequency of app use will be counted each time a participant opens the app.

Table 3. Study Measures

Tool		Measurement Time Points
Demographic Variables and Potential Confounders		
Socio-demographic characteristics	Gender, age, education, income, employment, health insurance, housing	Baseline
Behavioral Data	Use of condoms, tobacco, alcohol, substance use	Baseline, 3 and 6 months

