We will also use additional measurements of medication adherence to validate the findings from the CleverCap™ Lite dispenser. We will do blood draws at baseline, 3 and 6 months to measure CD4 and viral load data on each study participant; alternatively, participants will be given the option of providing recent lab results of their CD4 and viral load data. The blood draw at baseline will also be tested for genotyping, GSA chip and qPCR, Hormone blood levels (Estrogen and FSH), and cytokine blood levels (IL-1 β , IL-2, IL-4, IL-6, IL-8, IL-10, IL-13, TNF α , and CRP). The genotyping with GSA chip and qPCR, cytokine blood level and CRP, and hormone blood tests will only be collected once during the course of the study, at Baseline or at the 6-month follow-up if not completed at Baseline. The genotyping, GSA chip and qPCR will be performed by the Feinstein Institute for Medical Research at Northwell Health. We will also ask participants to complete the Center for Adherence Support Evaluation (CASE) Adherence Index, a simple composite measure of self-reported antiretroviral therapy (ART) adherence⁸¹. The CASE Adherence Index consists of three unique adherence questions. Past research has shown that the CASE Adherence Index correlated strongly with the three-day self-reported adherence data ($p<0.001$) and was more strongly associated with HIV outcomes, including a 1-log decline in HIV RNA level (maximum OR=2.34; $p<0.05$), HIV RNA<400 copies/ml (maximum OR=2.33; $p<0.05$) and performed as well as the three-day self-report when predicting CD4 count status. The CASE Adherence Index is an easy to administer instrument that provides an alternative method for assessing ART adherence in clinical settings. Items are scored such that higher values indicate better adherence, and the maximum total score is 16. Scores of 11 or higher on this index indicate good adherence (Cronbach's $\alpha=0.79$)⁸⁶.

Our primary outcome is ART adherence. The CleverCap™ Lite dispenser is our objective measure of ART adherence and the CASE Adherence index as a subjective measure. We are including the subjective measure since there is potential bias in that participants' in the control group may not use the device or may not use the device for the entire study period.

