We will assess for contamination between the study groups at the end of the trial by asking control group participants whether they had used any HIV or medication related apps in the past 6 months. In addition, participants will return at 3 and 6 months to complete the remainder of the measures listed in Table 3 and included in the Appendix. We will also collect data on app use through automated log files so there will not be response burden associated with this measure.

Secondary Outcome Measures: Our measures are listed in Table 3 and included in the Appendix.

D.9. Data Analysis.

We will use intention-to-treat principles for the primary outcome analysis. Intention to treat implies all subjects are considered in analyses. The outcome variable y_{-i} will be the total number of times the CleverCap™ Lite dispenser is opened at day t (from day 1 to day 180) for person i , so y_{-i} follows binomial distribution with parameter of p_{-i} and n where p is probability of taking medication (adherence rate) and n is number of medications to take each day. We use a generalized linear mixed model (GLMM) with logit link function to analyze adherence rate. The basic form of the model is: $\log(p_{-i}/(1-p_{-i})) = \beta_0 + \beta_1 t + \beta_2 t \times \text{INT} + \mu_{-i}$. In the model, μ_{-i} is person level random effect and follows normal distribution. This model is also called individual growth model. Independent variable INT is an indicator for intervention group (INT=1 for the intervention group and INT=0 for the control group). Regression parameter β_1 is change in adherence rate for the control group and β_2 is the difference in change in adherence rate between the intervention group and the control group.

This model can include personal level factors as covariates so we can test for potential confounding by covariates (i.e., age, gender, and health literacy) in this model and inspecting for changes in the point estimate of the relation between study group and adherence.

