We will use GLMM for analyzing secondary outcomes. In our analysis of the surveys related to the SDT framework, the variable time (t) will be at 3 time points (baseline, 3 month, and 6 month) and the link function will be identified for continuous outcomes. In the analysis of app use, the unit of analysis will be at daily level for each participant, and system use will be analyzed using a GMMM with log link function (Poisson model). For the analysis of CD4 and viral load, we will analyze difference-in-difference using GLMM with identity or log link function when these variables are treated as continuous outcomes. Viral load will also be treated as a binary outcome (detectable vs. undetectable) and analyses of viral suppression will use the GLMM with logit link. In a secondary “as treated” analyses, missing adherence and viral load data will be ignored. The genotype analysis will be run by the Feinstein Institute for Medical Research at Northwell Health. Finally, we will assess the relationship between adherence (independent variable) and virologic suppression (dependent variable) using GLMM logistic regression and including missing viral load as detectable. This model will include personal level factors as covariates so we can test for potential confounding by covariates (i.e., age, gender, and health literacy) in this model and inspecting for changes in the point estimate of the relation between study group and adherence.

E. Aim 2b: Assess the acceptability of the CleverCap™ dispenser through In-depth interviews, which will focus on the individual experience of PLWH with the device.

E.1. Sample. At the 3-month follow-up visit, semi-structured in-depth interviews will take place with participants in the intervention group. These participants will be the same participants from the intervention study arm, if they choose to participate (N=100)

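### No rule separates an unused bottle from a missed dose: part-way non-use by controls would bias the primary result towards the app, and the printed model understates its standard error

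*Combined protocol and SAP*

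**What the plan says.** - **Outcome.** D.8 reads the daily count of openings as the number of times medication was taken. D.9 models how often the "dispenser is opened at day t (from day 1 to day 180") as binomial, with n the number of medications per day. The printed equation is logit(p) = b0 + b1·t + b2·(t × INT) + a person-level random effect. The effect of interest is b2. There is no INT main effect and no random slope.
- **Analysis set.** D.9: "Intention to treat implies all subjects are considered in analyses".
- **Recognised threat.** D.8 adds the self-reported CASE index because participants "in the control group may not use the device or may not use the device for the entire study period". CD4 and viral load are collected to validate the bottle data, and Table 3 lists all three under the primary outcome.
- **Missing data.** In a secondary as-treated analysis, "missing adherence and viral load data will be ignored" (D.9). Missing adherence is not defined.
- **Reminders.** C.1: "If the Wise App does not receive notification that the pill bottle has been opened, additional reminders will be launched on the phone". D.7: "Those in the intervention group will receive medication reminders while those in the control group will receive reminders about completing their step goal".
- **Calls.** In D.7 both arms "will also receive a telephone call from a research assistant 1 week after enrollment to assist with any technical problems", then biweekly. Recording non-use is not given as a purpose.

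**The concern.** A day with no opening can mean a missed dose, a dose taken from another container, or a bottle put away. The outcome does not distinguish these, and two analysts could code the same log differently. The arms also differ in the prompt to open the bottle: only the intervention arm is reminded again while it stays shut. A difference in bottle use could therefore be reported as a difference in ART adherence.

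A second fault does not need the arms to differ. Someone who stops using the bottle moves from their usual level to zero and stays there. A model with only a person-level intercept treats that person's later zeros as separate pieces of evidence about slope, so the standard error of b2 is too small.

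**Working it through.** **1. The plan's own figures (D.4).** 200 randomised with 25% attrition leaves 75 per arm; two-sided alpha 0.05, one dose a day. Power is 90.7% for 80% v 86% and 88.6% for 84% v 89%. With effective n = 75 × 180 / (1 + 179 × ICC), 90.7% needs ICC 0.084 and 88.6% needs 0.075. No ICC is stated, so the figures are neither confirmed nor refuted. Only the effect sizes, 6 and 5 points, are used below.

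**2. Size of the false gap.** Let qC and qI be the shares that have stopped using the bottle by day 180, and a the true adherence of those people. Zero coding removes q × a from each arm, so

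false gap at day 180 = (qC − qI) × a.

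Setting this to 5 and 6 points gives the excess stopping needed:

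| a | for 5 points | for 6 points |
|---|---|---|
| 80% | 5/0.80 = 6.25 | 6/0.80 = 7.5 |
| 60% | 8.3 | 10 |
| 40% | 12.5 | 15 |

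An excess of 7.5% is about 6 of 75 people.

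**3. Zero against missing coding.** With users at 80%, setting non-use days to missing has error −(qC − qI) × (80% − a). At 12% v 5% stopping (control v intervention), in points:

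| a | zero | missing |
|---|---|---|
| 80% | +5.6 | 0 |
| 60% | +4.2 | −1.4 |
| 40% | +2.8 | −2.8 |
| 0% | 0 | −5.6 |

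The two errors are equal in size when a = 80% − a, that is, at 40%.

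**4. Simulation of the printed model.** Assumed: 75 per arm, one dose a day, 80% adherence with no true effect, stoppers still taking pills as before, random-intercept SD 1.0, stop day uniform, t scaled 0 to 1, days grouped into bins for fitting. The chance of falsely favouring the intervention should be 2.5%. Rows use 200 to 1,000 trials.

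| Non-use, control v intervention | mean b2 | result |
|---|---|---|
| none | 0.00 | 3% favour intervention (robust SE) |
| stop part-way 12% v 5%, coded zero | 0.39 | about 75% (model SE); 26% (robust SE) |
| same, coded missing | 0.00 | 2% (robust SE) |
| never used 15% v 5% | 0.03 | 4% (robust SE) |
| steady scattered days 12% v 5% | 0.11 | 21% (robust SE); 3% once an INT main effect is added |
| early, fading scattered days 12% v 5% | −0.35 | 88% favour **control** (robust SE) |
| stop part-way 10% v 10% | not used | any rejection: 45-50% (model SE); 4.5-6% (robust SE); 4.5% (random slope) |

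For scale, 80% to 86% is ln(0.86/0.14) − ln(0.80/0.20) = 1.815 − 1.386 = 0.43 on the logit scale, so the 0.39 in the second row is close to the planned effect.

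**5. Hand check on the variance.** At 10% v 10% the empirical SD of b2 is 0.295, the mean model SE 0.108 and the mean robust SE 0.302. A nominal 1.96 is then really 1.96 × 0.108 / 0.295 = 0.72 standard deviations, which gives about 47% two-sided rejection and agrees with the simulation.

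**6. Sensitivity to the random-intercept SD.** With 6 of 75 controls stopping and nobody in the intervention arm, SDs of 0.5, 1.0 and 2.0 all give a false gap of 5.6 to 5.8 points over the last 30 days.

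**The case against.** The authors saw the threat. They named it, added CASE because of it, planned CD4 and viral load as validation, and provided calls in both arms. That stands as a way to notice a problem. But none of these measures changes the primary estimate, no rule says what happens if they disagree with the bottle, and the as-treated analysis is secondary and rests on an undefined term.

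Stopping the bottle may also mean stopping pills. On one of the two qualifying routes in D.2, "participants must report past 30 days adherence of 80% or less", so low adherence among non-users is plausible. This stands: if a = 0, zero coding is right and missing coding errs against the intervention.

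D.9 calls its equation the basic form and a growth model, so a random slope may have been intended. That is possible, but none is written.

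A reader might infer that any extra unused days among controls favour the app. They do not. Controls who never use the bottle barely move b2. Scattered non-use favours the intervention only if steady or rising; if it is heaviest early and then fades, the sign reverses. The steady case arises because the printed equation lacks an INT main effect. Nor does the plan prescribe zero for non-use days; that is the literal reading of the outcome.

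**Conclusion.** The concern holds as a conditional gap that should be fixed, with medium confidence. If more controls stop using the bottle part-way while still taking pills, and those days count as zero, b2 is biased towards the intervention by the excess share stopping times those people's true adherence. At 80% adherence an excess of 6.25 to 7.5 percentage points matches the plan's 5 to 6 point effects. At 12% v 5%, about 75% of simulated trials falsely favour the intervention with the model's own standard error, and about 26% with a robust one. Correcting the variance therefore does not remove the bias.

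The variance fault is separate: equal 10% stopping in both arms takes the two-sided error rate from 5% to 45-50%.

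A reader might infer that this trial's result is inflated, or that its power figures are wrong. The documents support neither: they give no non-use rates and no ICC. The stopping rates and random-effect SD here are assumptions, and the rejection rates assume that stoppers keep taking pills as before.

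**What to change.** 1. **Model.** Use person-level robust standard errors or a random slope for time, and add an INT main effect. Cost: wider standard errors. With 10% stopping in both arms and zero coding, simulated power for the 80% to 86% example is about 20%, against 96% with those days set to missing and 98% with no non-use (robust SE).
2. **Definition of non-use.** Pre-specify an arm-neutral definition, applied to the dispenser log without knowledge of arm and supported by one bottle-use item on the existing biweekly calls in both arms. Report non-use by arm. Cost: one call item, which is unmasked self-report; no new visits.
3. **Coding.** Name one coding in advance. The literal zero can remain primary if the sponsor wishes, with non-use days set to missing as the sensitivity analysis. Add a tipping-point analysis that varies non-users' adherence separately by arm, for example over 40-80%. With users at 80% and 12% v 5% stopping, the observed 5.6-point gap then corresponds to true differences from −2 to +4.8 points. Cost: the log cannot tell a long lapse from non-use, so some true lapses may be coded missing.
4. **Denominator.** D.9 defines n by medications, while D.4 and D.8 count dosing occasions. Reconcile the wording and cap daily openings at n so that the binomial model is valid. Cost: wording only.

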1) The Comprehensive Health Program at Columbia University/NewYork-Presbyterian Hospital provides primary care, HIV specialty care and care coordination services to over 2,000 PLWH. 95% of individuals are of either Black or Latino background and women represent half of the overall population. In addition, the program has 28 direct clinical providers, 8 social workers, and 10 additional care coordinators. Of note, [name] (Co-I) is an attending physician at the Clinic.

2) AIDS Service Center (ASC) is a community based organization for PLWH and persons at risk for HIV. ASC has more than 90 staff, 85 peer interns, and more than 1,800 clients who come for services each year. In addition, another 18,000 people are reached through the peer education and community outreach initiatives of ASC. Given our past experience and success in recruiting participants and using the recruitment strategies described above, we are confident that we will be able to recruit the number of participants needed to conduct the study within the study timeframe. See details in Section A.3.3. Preliminary Work.

STATISTICAL PROCEDURES

D.4. Power and Sample Size.

We will recruit 200 individuals and have greater than 80% power to detect a less than 10% difference in adherence to ART medications between the Wise App and the control group. We assume a 25% attrition rate by the end of trial for both arms. The power calculations are based on the analysis of main outcome, ART adherence. All calculations are based on 2-sided test with alpha at 0.05 level. Our calculations are based on the assumption that each person is on a once daily regimen and the adherence rate is $\leq 80\%$ at baseline.

Many of our participants will be on regimens that are two or three times per day which will provide greater power for our study since we have a greater number of measurements (e.g., 180 for once daily vs. 360 for twice daily regimen). To illustrate, if the adherence rate for the control group does not change, we will have 90.7% power to detect a 6% increase in ART adherence for the intervention group (e.g., from 80% to 86% at

Table 2. Comparison of Intervention vs. Control Group

	Intervention	Control
The Wise App • Medication reminder • Step Goal reminder	✓ ✓	✓
CleverCap™ Lite dispenser	✓	✓

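### D.9 counts every dispenser opening as a binomial success but sets no upper bound, so a day with one surplus opening cannot be fitted and the plan gives no rule for it.

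*Combined protocol and SAP*

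**What the plan says.** The outcome and its denominator are described in three sections of the combined protocol and SAP.

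- **D.9 (Data Analysis).** The outcome y "will be the total number of times the CleverCap™ Lite dispenser is opened at day" t. It is taken to be binomial with probability p, the adherence rate, and size n, where n "is number of medications to take each day". The model is a logistic mixed model with a person-level random intercept, and its treatment term is time by intervention.
- **D.8 (Operationalization of Outcome Measures).** The device "will automatically record each time a participant opens the dispenser". Of the adherence data, D.8 says "it is a count response (number of times taking medication each day"). It gives no denominator.
- **D.4 (Power and Sample Size).** Measurements are counted as "180 for once daily vs. 360 for twice daily regimen", and the section adds that "Many of our participants will be on regimens that are two or three times per day".

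No section bounds y at n, merges repeat openings, or says what happens to a day on which openings exceed n.

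**The concern.** There are two linked problems, and the second is the more serious.

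The first is the unit of n. An opening is a dosing event, not a medication. Read literally, one drug taken twice daily gives y = 2 with n = 1 under perfect adherence. Two drugs taken together at one opening give y/n = 1/2 under perfect adherence.

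The second remains after n is read as doses. Because y counts every opening, all doses taken plus one extra opening gives y > n. A binomial count cannot exceed its size, so that record has zero likelihood. Someone must then choose a rule during analysis: set y to n, drop the day, or something else. The reported adherence level on the primary endpoint depends on that choice, which could be made after the data have been seen by arm.

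**Working it through.** **The plan's own count.** D.9 runs from day 1 to day 180. One dose a day gives 180 × 1 = 180, and two give 180 × 2 = 360. D.4's figures are therefore dosing occasions.

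**Inputs.** Adherence of 80%, and 86% for the comparison arm, come from D.4. So do 200 participants and 25% attrition, which give 200 × 0.75 = 150 completers and 150 × 180 = 27,000 person-days. The rate of extra openings is not in the documents, so it is an assumption throughout.

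**Model A: extra openings follow taken doses.** Doses taken are m ~ Bin(n, 0.80). Extra openings are x ~ Bin(m, e) with e = 1%, 5% or 10%, and y = m + x.

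*Days with y > n.*
- n=1: 0.80e = 0.8%, 4.0% or 8.0%, which is 1.4, 7.2 or 14.4 of 180 days.
- n=2: 0.64[1 − (1 − e)²] = 1.3%, 6.2% or 12.2%.
- A once-daily participant has at least one such day with probability 1 − (1 − 0.80e)^180 = 76%, 99.9% or over 99.9%.
- Even at e = 0.1%, 27,000 × 0.0008 ≈ 22 such days are expected. With independent days, the chance of none is (1 − 0.0008)^27,000 ≈ 4 × 10⁻¹⁰.

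*Adherence level at e = 10% (true value 80%).*
- n=1, bounded: 0.80. Dropped: 0.80 × 0.90/(1 − 0.08) = 0.720/0.920 = 0.783.
- n=2, with P(m=1) = 0.32 and P(m=2) = 0.64. Bounded: (0.32 × 1.1 + 0.64 × 2)/2 = 0.816. Dropped: (0.32 × 1.1 + 0.64 × 0.81 × 2)/(2 × 0.8784) = 1.3888/1.7568 = 0.7905.
- n=3, with P(m=1) = 0.096, P(m=2) = 0.384 and P(m=3) = 0.512. Bounded: (0.096 × 1.1 + 0.384 × 2.19 + 0.512 × 3)/3 = 0.828. Days with y > n: 0.384 × 0.01 + 0.512 × 0.271 = 0.1426. Dropped: (0.096 × 1.1 + 0.384 × 2.16 + 0.512 × 0.729 × 3)/(3 × 0.8574) = 0.799.

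| n | Days with y > n | y set to n | Day dropped |
|---|---|---|---|
| 1 | 8.0% | 80.0% | 78.3% |
| 2 | 12.2% | 81.6% | 79.1% |
| 3 | 14.3% | 82.8% | 79.9% |

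**Model B: extra openings unrelated to doses.** These are Poisson at 0.10 per day, with n=1.
- Bounded: 1 − 0.20e^(−0.10) = 81.9%.
- Dropped: (0.0181 + 0.7239)/(0.1810 + 0.0181 + 0.7239) = 80.4%.
- Missed-dose days scored as adherent under bounding: 0.20 × (1 − e^(−0.10)) = 1.9% of days.

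**Contrast between arms, equal extra-opening rates.** The true logit difference is ln(0.86/0.14) − ln(0.80/0.20) = 0.429. The Model A rows use e = 10%.

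| Scenario | Bounded | Dropped |
|---|---|---|
| A, n=1 | 0.429 | 0.429 |
| A, n=2 | 0.430 | 0.415 |
| A, n=3 | 0.437 | 0.404 |
| B, n=1 | 0.421 | 0.420 |

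The largest shift under bounding is (0.4372 − 0.4290)/0.4290 = 1.9%. Under dropping it is (0.4290 − 0.4043)/0.4290 = 5.8%. These are cross-sectional contrasts. The effect on the planned time-by-intervention slope was not computed.

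**The case against.** The strongest reply is that the denominator question is mostly wording. D.4 counts dosing occasions, D.8 describes the count as times medication is taken, and D.9 calls p the probability of taking medication. Read together, these make doses the natural meaning of n. That stands, and only a clearer wording is needed there. A reader might infer that the plan truly intends to divide openings by the number of drugs. D.4 and D.8 make that unlikely.

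The reply does not supply a bound. D.8's description gives no rule for turning openings into doses, and D.9 still counts all openings.

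It can also be said that the failure is conditional on a surplus opening occurring, that no rate is documented, and that one line of data derivation repairs it. All of this is true. But the rate would have to be far below 0.1% per taken dose for the trial to escape the problem.

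A reader might go further and infer a biased treatment effect, because D.7 says "Those in the intervention group will receive medication reminders while those in the control group will receive reminders about completing their step goal". The documents give no opening rates by arm, so a difference in surplus openings is speculation. With equal rates the computed contrast moves little, and not at all for once-daily dosing under Model A.

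Nor do these results show that D.4's stated power is wrong. D.4 assumes one dose a day, and the documents give no within-person correlation with which to check its figures.

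**Conclusion.** The concern holds as a defect in the definition of the primary outcome. D.9 as written cannot accommodate a fully dosed day with a surplus opening, and the plan has no rule for one. The size of the effect rests on an assumed surplus rate. At 10%, the choice between bounding and dropping moves the reported level by 80.0 − 78.3 = 1.7 points for n=1, 81.6 − 79.1 = 2.5 points for n=2 and 82.8 − 79.9 = 2.9 points for n=3. For scale, D.4 plans around differences of 5 to 6 points between arms, although a shift in level is not a shift in that difference.

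The direction of the error depends on why extra openings occur. For n=1, bounding is exact under Model A, whereas under Model B dropping lies closer to 80%. Neither rule is uniformly better, which is the reason to fix one in advance. Bias between arms is not shown, and the effect on the planned slope is unknown. This should be corrected, but it does not invalidate the design.

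**What to change.** In D.9, with matching wording in D.8:

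- Define n as the number of scheduled ART dosing occasions for that participant-day, recorded in the same way in both arms.
- Define y as min(openings, n).
- Fix both definitions before outcome data are compared by arm.

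State the limits of bounding. An unrelated opening can make a missed dose count as taken at any n, including n=1 (1.9% of days under Model B). Repeated openings around one dose can do the same when n is 2 or more. For n=2 and e = 10% under Model A, 0.32 × 0.10 = 3.2% of days are scored as fully adherent although a dose was missed.

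Add a sensitivity analysis that uses the device's time stamps to merge openings closer together than a minimum gap, with the gap specified in advance. This addresses repeated openings. It does not remove an isolated opening on a day when the dose was missed, and the report should say so.

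The cost is one derivation step, the sensitivity analysis and the wording changes. D.9 already needs a value of n for every participant. The step to confirm is that it is collected alike in both arms, since C.1 mentions a schedule only for the reminder component ("Reminders will be tailored to participants' medication schedule"). No new visits or devices are needed.
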